PROTOCOL TITLE: Medical Marijuana Use and Driving Performance: A Test of Psychomotor Function in Adults 50 and Older.

visual channels form an immersive and realistic driving experience. A 5.1 channel audio system external to the car cab provides the environmental sounds such as traffic, passing vehicles, and road noise. An internal audio system to the car cab provides the engine sounds and vibrations, as well as pre-programmed voice commands and any other scripted sounds. A 4-door sedan allows the driver to operate normal accelerator, brake, steering, transmission selection, and signaling controls with the simulator responding accordingly. All driver inputs are controlled by software that interfaces with the electronics in the car cab. The adaptation scenario is standardized for older adults and has been used in our prior driving studies. The main drive consists of straight residential roadways connecting 8 left turns and 2 right turns with minimal ambient traffic. Three scripted events will be randomly presented to the drivers. To assess response time, a vehicle is pulling out in front of the driver and the driver's behavior is measured via braking (ms) and swerving (SD of lateral deviation from center lane). Next, divided attention is assessed via a diamond on the screen turning to a triangle and the participant needs to honk as soon as (s)he sees it (measured in ms and number of omissions and commissions). Lastly, executive functions are measured by providing the driver with an instruction before the drive (i.e. to turn into a McDonald's, pull into a parking bay, and when it is safe to do so, exit the lot and merge into the flow of traffic (measured via visual scanning (yes/no) speed regulation (mph over or under the speed limit), adjustment to stimuli (notice the McDonald's (yes/no), and slow down (mph), signaling (yes/no), vehicle positioning (buffer around the vehicle yes/no), and gap acceptance (narrow or tight via m/sec).

6.8 Adverse Effects: In this study, adverse effects are defined as undesired effect that occurs when the medical marijuana is administered. We will use Scripted Prompting, a proactive form of adverse effect capture recognized in the field. This method is designed to elicit adverse effects without biasing the patient; it is a standardized question that allows participant to report important symptoms without being influenced by suggestion. For this study we will ask: "*Since initiating medical marijuana, are you having any problems related to use?*"

6.9 Control Procedures: Control participants will be community-dwelling age, race, and gender matched.

6.10 Participant Retention: We will develop a strong collaborative relationship between participants and members of the research team through empathy, encouragement and skill building.

6.11 Three- and Six-Month Follow-Up Assessment: The second assessment (T2) will occur one month after the participant has been dispensed medical marijuana for the first time. T3 will occur 3 months after the participant has been dispensed medical marijuana for the first time. The follow-up assessments will consist of a minimally reduced psychosocial assessment battery, and the same simulator adaptation and main drive (described above). All participants will be paid \$50 per assessment visit (\$150 total across all visits over the 3 month period). Participants

**PROTOCOL TITLE:** Medical Marijuana Use and Driving Performance: A Test of Psychomotor Function in Adults 50 and Older.

will not be paid for screening assessments or chart abstracted data. Data will be collected using both self-directed methods such as ACASI with headphones or self-administered on paper and Research Assistant administered tasks. The Baseline Assessment is expected to take approximately 90 minutes, and follow-ups will take approximately 60 minutes. Though it is time-consuming, we do not anticipate participant barrier as a burden based on prior work.

[figure not shown]
**7.0 Data and Specimen Banking\***

N/A.

**8.0 Sharing of Results with Subjects\***

N/A.

**9.0 Study Timelines\***

9.1 Each subject will be enrolled for a total of 3 months and 1 week. The duration anticipated to enroll all study subjects is 12 months.

**10.0 Subject Population\***

10.1 We will recruit 60 patients from Medical Marijuana Treatment Clinics (MMTC) of Gainesville. The intervention group will be comprised of adults 50 and older who report severe or chronic pain, are newly registered for the Medical Marijuana Registry in the State of Florida, have no prior history of medical marijuana use, can communicate in English, and are willing and able to complete study procedures. The control group will be age, gender, and race matched.

10.2 Inclusions and Exclusions of Special Populations

- 10.2.1 Adults unable to consent will be excluded from the study.
- 10.2.2 Individuals who are not yet adults (infants, children, teenagers) will be excluded from the study.
- 10.2.3 Pregnant women will be excluded from the study.
- 10.2.4 Prisoners will be excluded from the study.

**11.0 Vulnerable Populations\***

N/A

**12.0 Local Number of Subjects**

12.1 N = 60

**13.0 Recruitment Methods**

13.1 We will recruit patients using convenience sampling technique from Medical Marijuana Treatment Clinics (MMTC) of Gainesville.

PROTOCOL TITLE: Medical Marijuana Use and Driving Performance: A Test of Psychomotor Function in Adults 50 and Older.

## **14.0 Withdrawal of Subjects\***

14.1 The Principal Investigator can withdraw participants from this study for unanticipated reasons.

## **15.0 Risks to Subjects\***

15.1 Questions may be unpleasant or difficult for participants to answer. Additionally, despite taking appropriate steps to safeguard collected information, there is a slight risk that participant information could be revealed accidentally or inappropriately. This release of information may upset a participant or even affect their insurability or employability. A Certificate of Confidentiality issued from the National Institute of Drug Abuse will assist us in protecting participant information.

## **16.0 Potential Benefits to Subjects\***

16.1 Participants will not directly benefit from this study.

## **17.0 Data Management\* and Confidentiality**

17.1 **Test of Aim 1 (Driving Simulator):** Between group (medical marijuana users vs controls) comparisons will first be examined using independent samples t-test (controlling for unequal variances using Levene's test) or Mann-Whitney U tests if the data are nonparametric. Repeated measures ANOVA will be used to examine within participants differences on measures at all 3 time points in order to answer the question of whether medical marijuana impacts response time, divided attention, and executive functions.

Limitations may be related to the distribution of the dependent and independent variables. Possible mitigation approaches include creating a dichotomous variable of high versus low for outcomes and using logistic regression or other functional form as dictated by the distribution of the dependent and independent variables.

17.2 **Test of Aim 2 (Adverse Effects):** To describe factors associated with adverse effects we will report the number of adverse effects reported by participants at time points 2 and 3. Adverse Effects will be defined as both a count variable and a binary variable such that absence or presence of adverse effects will be coded as 0/1 respectively. We will then use Poisson and Logistic regression methods to examine analyze the bivariate association between dosage, frequency of use, route of administration (pills, vape, etc.), and type of product (THC v. CBD). Limitations may be related to the frequency and distribution of events leading to complete or quasi-separation of data points. Possible mitigations would be re-categorization of explanatory variables, exact or firth regression, or a different functional form of the model. The goal of aim 2 is to examine the strength of the association between factors of medical marijuana use and adverse effects. As there may be insufficient power for statistical

PROTOCOL TITLE: Medical Marijuana Use and Driving Performance: A Test of Psychomotor Function in Adults 50 and Older.

significance, effect size estimates (Cohen's d) will be used to examine the strength of the association between variables.

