We will recruit N=60 participants total. Participants will be eligible for the current study if they: a) report severe or chronic pain; b) are age 50 or older; c) are newly registered for the Medical Marijuana Registry in the State of Florida; d) have no prior history of medical marijuana use; e) can communicate in English; and f) are willing and able to complete study procedures or if they meet control group criteria: (n=30) Medical Marijuana Users **or** (n=30) Age, Gender, Race Matched Controls. Persons will be ineligible if they: a) meet

**PROTOCOL TITLE:** Medical Marijuana Use and Driving Performance: A Test of Psychomotor Function in Adults 50 and Older.

criteria for current or past alcohol and/or illicit drug dependence; b) have vertigo or any vestibular systems dysfunction (due to the to develop simulator adaptation syndrome); c) screen high on the simulator sickness prescreen; d) use contraindicated medication (benzodiazepines, beta blockers, antihistamines, or sedatives) from which they cannot abstain due to medical reasons; and/or e) are planning to move out of the area within 6 months.

We will recruit patients in the control group within the local community. This will happen by placing recruitment flyers in public places (i.e. grocery stores, libraries, senior living communities, etc.). Additionally, we will utilize Consent2Share, an initiative of the UF Integrated Data Repository (IDR) and supported by UF CTSI (Clinical and Translational Science Institute) that allows for a large group of potential research participants who have consented to be re-contacted for future research studies. The control group will be matched by age, gender and race. Control subjects will be ineligible if they: a) meet criteria for current or past alcohol and/or illicit drug dependence; b) have vertigo or any vestibular systems dysfunction (due to the to develop simulator adaptation syndrome); c) screen high on the simulator sickness prescreen; d) use contraindicated medication (benzodiazepines, beta blockers, antihistamines, or sedatives) from which they cannot abstain due to medical reasons; and/or e) are planning to move out of the area within 6 months, f.) have a history of marijuana use. Control subjects will be used to ensure results are not attributed to a simple change in time. Results will provide evidence for the effects of medical marijuana use on the real work task among adults 50 and older.

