### 17.3 Power Analysis

17.4 We compute the power to detect a medium effect size of 0.5 standard deviations across groups. Assuming a correlation of 0.2 across the repeated measures at three time points, the standard deviation of the average of three measures is 0.683 times the standard deviation of one measure. Therefore, with 31 per group we can detect a difference in this average of 0.5 times the standard deviation of one measure, using a two-sided test with 80% power. We calculated Cohen's d using [name] prior work that examined total driving errors and specific errors (Lane maintenance) in healthy controls ( $M= 24.08$   $SD=12.38$ ) and ( $M= 5.78$   $SD=4.26$ ) versus Parkinson patients ( $M=31.99$   $SD=22.01$ ) and ( $M=10.23$   $SD= 9.26$ ) which yielded a Cohen's d of .46-.65 (medium effect size); therefore we will be powered to detect this medium effect size.

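### Controls are matched on age, gender and race, but no Aim 1 analysis uses the matching or adjusts for those factors; adjusting would give a modest gain in precision at almost no cost.

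*Combined protocol and SAP*

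**What the plan says.** Section 6.1 states "The control group will be matched by age, gender and race" and "We will recruit N=60 participants total", split as 30 users and 30 controls. Sections 1.1.2, 5.1, 6.9 and 10.1 also describe the controls as matched on these three factors. None of them says whether each control is matched to a particular user or the groups are balanced overall, and no caliper or match identifier is given.

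For Aim 1, section 17.1 begins: "Between group (medical marijuana users vs controls) comparisons will first be examined using independent samples t-test", with Mann-Whitney U as the alternative. It continues: "Repeated measures ANOVA will be used to examine within participants differences on measures at all 3 time points". Neither step mentions a pair term or adjustment for age, gender or race.

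The power statement in section 17.4 says "We compute the power to detect a medium effect size of 0.5 standard deviations across groups" and refers to the average of the three visits. It gives 31 per group for 80% power, two-sided.

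**The concern.** Matching on factors related to the outcome makes the two groups more alike than two unrelated samples. An independent-samples test does not know this: its standard error still contains the variance that the matching factors explain. This applies to either form of matching. With one-to-one matching the test ignores the correlation between partners; with frequency matching it leaves explained variance in the error term.

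A relation between age and the outcomes is plausible on the protocol's own reasoning. Eligibility starts at 50 with no upper limit, and section 3.0 argues that intersections and merges tax older drivers' cognitive, sensory and motor abilities. What is at stake is precision: the study takes on the work of matching during recruitment and may not collect the benefit in its analysis.

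**Working it through.** **Inputs.** From the documents: 30 per group (6.1); difference of 0.5 SD of one measure, within-person correlation of 0.2 and three visits (17.4). Assumed: alpha 0.05 two-sided, which is not stated; rho, the correlation between matched participants (roughly the share of outcome variance that the matching factors explain), which is not given and is varied.

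**Step 1: the plan's own figure.** The SD of the three-visit average is sqrt((1 + 2 × 0.2)/3) = 0.683, as stated ("the standard deviation of the average of three measures is 0.683 times the standard deviation of one measure"). For two independent groups, a difference of 0.5 and SD 0.683, the exact noncentral-t calculation gives 80.9% power at 31 per group and 79.6% at 30. The stated 31 therefore reproduces with the independent-groups formula, so the power calculation does not use the matching either.

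**Step 2: how large rho can be.** Section 17.4 is explicit: "Assuming a correlation of 0.2 across the repeated measures at three time points". If visits are equally correlated, stable differences between people make up 20% of single-visit variance. Age, gender and race are stable traits and can explain at most that part, so rho is capped at about:
- 0.2 for a single visit;
- 0.2/0.467 = 0.43 for the three-visit average, whose variance is 1.4/3 = 0.467.

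**Step 3: standard error and type I error.** The unadjusted standard error is too large by 1/sqrt(1-rho): 1.054 at rho 0.1 and 1.118 at rho 0.2. In simulation with 30 pairs (60,000 runs per setting), the true two-sided type I error of the independent t-test was about 4.0% and 2.9%, against a nominal 5%.

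**Step 4: power on the three-visit average, 30 per group.** The unpaired figures at rho above 0 are simulated. The others use the noncentral t with noncentrality 0.5/(0.683 × sqrt(2(1-rho)/30)), which is 2.83, 2.99 and 3.17 at rho 0, 0.1 and 0.2. The paired test has 29 degrees of freedom. The adjusted model has 60 - 2 - 3 = 55, counting one covariate degree of freedom each for age, gender and race.

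| rho | Unpaired | Paired | Covariate-adjusted |
|---|---|---|---|
| 0 | 79.6% | 78.2% | 79.5% |
| 0.1 | 80.8% | 82.3% | 83.5% |
| 0.2 | 82.1% | 86.5% | 87.6% |

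The adjusted column assumes that the covariates remove the whole share rho.

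**Step 5: a single visit.** Section 17.1 does not say that the t-test is applied to the three-visit average. At one visit (SD 1), with rho 0.1, power is about 48% unpaired, 51% paired and 52% adjusted. Most of the fall from about 80% comes from using one visit instead of three, not from ignoring the matching.

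**The case against.** The strongest reply has four parts.

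- **Pairs are not documented.** Controls come from flyers and a re-contact registry, which fits group-level matching as well as pairing. This stands, and it is why covariate adjustment, which suits both forms, should be the main request. A reader might infer that the independent t-test loses power as a matter of fact. The documents do not support that: it depends on a positive rho that they do not give. At rho 0 the paired t-test is about 1.4 points worse, because it has 29 rather than 58 degrees of freedom.
- **The correlation must be small.** A reader might apply rho 0.3 to a single visit and infer a standard error 20% too large and 61% power with pairing. That conflicts with section 17.4: strangers matched on three traits would resemble each other more than a participant resembles himself or herself at another visit. This part stands in full.
- **The t-test is only the first look.** Section 17.1 relies on the repeated measures ANOVA to answer the main question, and section 6.1 says controls are there to rule out a simple effect of time. In change over time, stable age, gender and race differences largely cancel, so the gain would be smaller. This stands, but the ANOVA as described does not use the matching factors either.
- **The error is conservative.** This stands. No bias and no excess of false positives follows from this point.

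None of these parts removes the mismatch between a matched design and an analysis that ignores it.

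**Conclusion.** The mismatch is real and its consequence is modest. If the matching factors predict driving performance, the planned between-group test is conservative. On the three-visit average, the power forgone relative to an adjusted analysis is about 3 points at rho 0.1 and 5 to 6 points at rho 0.2. Relative to a paired test it is about 1.5 and 4 points. These figures rest on assumed values of rho, alpha 0.05, 30 per group with complete data, and the plan's own correlation of 0.2.

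A reader might also infer that ignoring the matching leaves the study short of its stated power. It does not. The difference between 79.6% and 80.9% arises from planning 30 rather than 31 per group. Where rho is positive, the unpaired test's power at this effect size rises slightly rather than falls. The loss is only relative to a better analysis. The case for change is that the improvement is nearly free, not that the plan is invalid.

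**What to change.** In section 6.1, state whether matching is individual or by frequency. In section 17.1, adjust the between-group comparison and the repeated measures model, with group included as a factor, for age (continuous), gender and race. If matching is one-to-one, record the match identifier at enrolment and use a mixed model with a matched-pair random effect; this still uses a participant whose partner drops out. Keep the unadjusted t-test or Mann-Whitney test as descriptive only.

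The cost is a change of SAP wording, one extra recorded field if matching is individual, and about three degrees of freedom (more if race is kept in several categories). If the factors explain nothing, adjustment loses about 0.1 point of power.

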#### **4.1.1 Response Time**

Type: Primary

Time Frame: Baseline (T1), 1 Month (T2) and 3 Months (T3)

Brief Description: After the first 5-minute acclimation scenario, the driver will drive the main drive for another 15 minutes. The first 7 minutes of the drive will include daytime driving, start in a rural area with some ambient traffic, rolling hills, curves in the road, and include the occasional lead vehicle, oncoming traffic, and some vehicles behind the driver. Data will be collected via the kinematic functionality of the high-fidelity driving simulator (e.g. speed in mph, braking, swerving, lateral lane positioning, etc.) and also through observing the performance of the driver -- for yes/no responses – via a trained evaluator who will use the playback function of the simulator to scrutinize the errors. To assess response time, a vehicle is pulling out in front of the driver and the driver's behavior is measured via braking milliseconds (ms) and swerving (SD of lateral deviation from center lane).

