#### **4.1.2 Divided Attention**

Type: Primary

Time Frame: Baseline (T1), 1 Month (T2) and 3 Months (T3)

Brief Description: Data will be collected via the kinematic functionality of the high-fidelity driving simulator and observation. During the course of the main drive consisting of straight residential roadways connecting 8 left turns and 2 right turns with minimal ambient traffic using an established protocol, during the course of the drive divided attention (being aware of the traffic and surrounding while focusing on critical stimulus) is assessed

PROTOCOL TITLE: Medical Marijuana Use and Driving Performance: A Test of Psychomotor Function in Adults 50 and Older.

via a diamond on the screen turning to a triangle and the participant needs to honk (i.e. respond) as soon as (s)he sees it (measured in ms and number of omissions and commissions).

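### Section 17.1's first listed mitigation for distributional problems in the primary driving outcomes is a high/low split with no cut-point, trigger or within-person term, which costs power and leaves the cut open to choice after the data are seen

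*Combined protocol and SAP*

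**What the plan says.** Section 17.1 sets out the Aim 1 analysis in two steps. The groups are first compared by t-test, "or Mann-Whitney U tests if the data are nonparametric". Then "Repeated measures ANOVA will be used to examine within participants differences on measures at all 3 time points", and this second step is the one meant to answer whether medical marijuana affects the three driving domains.

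A separate paragraph deals with distributional trouble. The first option it lists as possible is "creating a dichotomous variable of high versus low for outcomes and using logistic regression", beside some other functional form, with the choice to be made "as dictated by the distribution of the dependent and independent variables". The document states no cut-point for high versus low, no criterion for leaving the planned analysis, and no rule for choosing among the options. The logistic model is named without a random effect, GEE or other within-person term.

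The outcomes concerned are all labelled primary. Response time is "measured via braking milliseconds (ms) and swerving (SD of lateral deviation from center lane"). Divided attention is "measured in ms and number of omissions and commissions". Executive functions (section 4.1.3) mix speeds in mph and gap acceptance with items recorded yes/no: visual scanning, noticing the target, signalling and vehicle positioning.

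**The concern.** Splitting a graded measurement into two classes treats every driver on the same side of the cut as identical. The study was sized in section 17.4 on a continuous three-visit average, with no allowance for that loss.

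Two further things are at stake. First, with neither cut nor trigger fixed, the analyst can see the data before deciding whether to split and where, so the nominal error rate of a primary test is no longer assured. Second, each person contributes three visits. If each visit is split and entered in an ordinary logistic regression, the rows are treated as independent, although section 17.4 itself assumes they are correlated.

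**Working it through.** **Inputs.** From section 17.4: difference 0.5 SD of one measure, correlation 0.2, three time points, two-sided test, 80% power, 31 per group. From section 6.1: 60 participants, 30 per group. Alpha is not stated; 0.05 is assumed.

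**The plan's own figure.** SD of the three-visit average = sqrt((1 + 2 × 0.2)/3) = 0.683, as stated. Normal approximation: n = 2 × (1.960 + 0.842)² × (0.683/0.5)² = 29.3, so 30 per group; the noncentral t calculation gives 31. The sizing reproduces. The standardised difference on the average is 0.5/0.683 = 0.732. Keeping the outcome continuous, 30 per group gives t-test power of 0.796.

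**Median split of the average, normal data.** The pooled median lies midway between the groups, so the proportions classed high are Φ(−0.366) = 0.357 and Φ(0.366) = 0.643. Power = Φ[(√30 × 0.286 − 1.960 × √0.5)/√(2 × 0.357 × 0.643)] = Φ(0.26) = 0.60. Reaching 80% would need 47 per group (54 with continuity correction).

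The large-sample efficiency of a median split is 2/π = 0.64, so 30 per group acts like 19.1; a t-test with 19 per group has power 0.59, which agrees.

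**How far the test matters.** Simulation, 20,000 trials, 30 per group:
- t-test on the undivided average: 0.80; Mann-Whitney: 0.77.
- Median split, uncorrected chi-square: 0.67, but with type I error about 0.07. Fisher's exact test: about 0.46-0.47.
- Each visit split at its median and each person's proportion of high visits compared: about 0.65, with type I error about 0.05.

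Hence the range of 60-67%, with Fisher below it.

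**Other cuts** (same formula, normal data):

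| Cut (pooled percentile) | Proportions high | Power, 30 per group | n per group for 80% |
|---|---|---|---|
| 50th | 0.357 / 0.643 | 0.60 | 47 |
| 67th | 0.202 / 0.458 | 0.57 | 52 |
| 75th | 0.139 / 0.361 | 0.51 | 59 |
| 90th | 0.042 / 0.158 | 0.32 | 103 |

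**Choosing the cut afterwards.** With no group difference and the uncorrected test, one fixed median cut rejects in about 7% of trials. The best of the 50th, 67th and 75th percentile cuts rejects in about 13-14%, the best of the 25th, 50th and 75th in about 17%, and the best of seven cuts in about 22%.

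**Skewed data.** A median split is unchanged by a log transformation, so for a shift on the log scale the result above carries over. With lognormal data (log-SD 1, log shift 0.732 SD, 30 per group), simulated power is 0.60 for the raw-scale t-test, about 0.66 for the median split and 0.77 for Mann-Whitney. For a raw-scale location shift, the large-sample efficiency of the split relative to Mann-Whitney is 0.59 (lognormal, log-SD 0.5) and 0.40 (log-SD 1).

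**The case against.** The strongest case against has five parts.

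- **Mann-Whitney is already in the plan.** A reader might infer that splitting is the only or the first-named remedy in section 17.1. It is not: the rank test comes earlier, for the group comparison. What stands is that nothing comparable is offered for the repeated-measures analysis, which carries the Aim 1 question.
- **The split is only possible.** It sits beside another functional form, wording loose enough to admit the log-scale and count models proposed here. A reader might infer that the split is likely to be used, but no distribution of any simulator outcome in this population is given. The lane-maintenance figures in section 17.4 (5.78, SD 4.26; 10.23, SD 9.26) have SD/mean of 0.74 and 0.91. That suggests skew, but in another outcome and population. The open wording leaves the choice to the data and does not settle it.
- **A loss of about a third is not a property of the plan.** The 2/π result belongs to a median split of near-normal data, or of data that are normal after a log. The fallback is meant for awkward distributions. For strongly skewed data the split can beat the raw-scale t-test, as the lognormal case shows. Under a symmetric double-exponential distribution it is even more efficient than Mann-Whitney in large samples (ratio 1.33). That shape is hard to expect of outcomes bounded at zero; in the skewed cases examined the split loses to the rank test.
- **The clustering point depends on what is split.** If the three-visit average is split, there is one binary value per person and no within-person correlation to model. The missing term matters only if visits are split separately.
- **Some items are binary already.** For the yes/no items in section 4.1.3, a logistic model discards nothing.

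**Conclusion.** The point holds as a cheap improvement. As a listed option for primary outcomes, the split has no stated cut-point, trigger or within-person term. With the plan's own effect and correlation, 30 per group, alpha 0.05 and near-normal data, a median split takes power from about 80% to about 60-67%. Cuts away from the median generally lose more, and picking the best of three afterwards puts the false-positive rate at about 13-17%, part of which comes from the uncorrected test itself.

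The documents do not support the stronger conclusions that the split discards most of the measurement, that the study cannot keep its power, or that a fixed share of information will be lost. All three depend on an unstated cut and unknown distributions, and on the split being used at all. The firm comparison is with the better alternative: on skewed data a rank or log-scale analysis of the undivided outcome keeps power that the split gives up.

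**What to change.** In section 17.1, remove the high/low split for outcomes measured in ms, mph, lateral deviation or counts, and put in its place, before data are seen:

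1. If distributions are poor, analyse times and lateral deviation on the log scale within the repeated-measures model, or use a rank-based or bootstrap analysis of the undivided outcome.
2. Analyse omissions and commissions with a count model with participant-level clustering.
3. Keep binary models, with participant-level clustering, only for the executive-function items recorded yes/no in section 4.1.3.
4. State the criterion for moving from the planned analysis to a fallback.

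If the investigators wish to retain a split, its cut-point and trigger should be fixed in advance. That removes the analyst's freedom but not the power loss.

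The cost is SAP wording only; no data collection changes. The downside is that log-scale results are ratios of geometric means, not differences on the raw-SD scale used for sizing, and need a line of explanation.
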